#### 4.5 COMPLIANCE

Study treatment compliance will be summarized using the TTS. Treatment compliance will be presented at the patient level as described below. The term *Planned* refers to the treatment dose and frequency planned at enrollment. The term *Prescribed* refers to the treatment dose and frequency reported at each IMP course and infusion.

Compliance will be described at the course level using the following criteria:

- Prescribed course dose (g/kg) = Theoretical course dose (g/kg)  
Theoretical course dose is defined according to the protocol as 0.5 g/kg.
- Time since previous course = 3 weeks  $\pm$  7 days
- Courses administered within 1 to 2 days
- Duration of the flow rate of the first course infusion remains unchanged for at least 25 minutes
- Flow rate of the first infusion of a course  $\leq$  0.5 mL/kg/h

Compliance will be described by patients using the following criterion:

- Total patient compliance: A patient is compliant if all courses of the patient are compliant.

Non-compliant courses and infusions will be listed by patient showing all of the above criteria. The criterion leading to non-compliance will be flagged.

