#### **6.1.3. 4. Compliance**

Compliance with treatment is defined as dose(s) administered within 20% of the prescribed dose(s). Both prescribed and administered doses will be recorded in the eCRF.

As the study drug will be administered only under the direct supervision of a physician familiar with the requirements of the study protocol, compliance should not be an issue. Nevertheless, the reason for any non-compliance must be recorded in the eCRF.

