### **12.8.2. Treatment Compliance**

The following compliance criteria will be described:

- Prescribed course dosage included in the ranges allowed by the protocol
- Course frequency included in the ranges allowed by the protocol
- Courses administered at each visit.
- Ratio administered dose / prescribed dose within 20%.

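### SAP 4.5 leaves out the protocol's own compliance definition (administered within 20% of prescribed dose), undeclared, and tests the prescribed dose against 0.5 g/kg with no tolerance or rounding rule

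*SAP*

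**What the plan says.** Protocol 6.1.3.4 gives the definition: "Compliance with treatment is defined as dose(s) administered within 20% of the prescribed dose(s"). It adds that "Both prescribed and administered doses will be recorded in the eCRF", so the comparison can be made. Protocol 12.8.2 lists four criteria to be described: prescribed dosage within the permitted ranges, course frequency within the permitted ranges, whether courses were given at each visit, and "Ratio administered dose / prescribed dose within 20" per cent.

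SAP 4.5 lists five course-level criteria:

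- "Prescribed course dose (g/kg) = Theoretical course dose (g/kg"), with the explanation "Theoretical course dose is defined according to the protocol as 0.5 g/kg";
- an interval of 3 weeks ± 7 days since the previous course;
- "Courses administered within 1 to 2 days";
- an initial flow rate left unchanged for at least 25 minutes;
- a flow rate in the first infusion no higher than 0.5 mL/kg/h.

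At patient level, "A patient is compliant if all courses of the patient are compliant". The SAP says that the term Prescribed "refers to the treatment dose and frequency reported at each IMP course and infusion".

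SAP 4.10, which records changes to the planned analysis, does not mention compliance.

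**The concern.** The one comparison that the protocol uses to define compliance is absent from the SAP section that implements it, and nothing tells the reader that it was removed. Protocol 12.2 expects departures to be discussed in the study report; one that SAP 4.10 does not list is easily missed there.

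What remains is a test of the prescription, written as an equality. The SAP gives the interval criterion a margin of 7 days but gives the dose criterion none, and it does not say to how many decimals the two doses are compared.

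This matters more than usual for a compliance table. The study examines a reduced dose, and SAP 4.10 reports early termination because a notable share of patients relapsed on it. Readers will ask whether those patients received the planned dose, and the compliance table is where they will look first.

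**Working it through.** The plan states no compliance rate, so there is no figure to reproduce. Two checks apply.

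**1. The two dose rules on example courses.** Inputs: the theoretical dose of 0.5 g/kg (SAP 4.5) and the 20% margin (Protocol 6.1.3.4). The SAP rule is prescribed = 0.5. The protocol rule is 0.80 ≤ administered/prescribed ≤ 1.20, which for a prescription of 0.5 g/kg means 0.5 × 0.8 = 0.40 to 0.5 × 1.2 = 0.60 g/kg administered. Prescribed is read here as the ordered dose, because the protocol records the two doses as separate eCRF items.

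| Prescribed / administered (g/kg) | Ratio | SAP dose criterion | Protocol ratio |
|---|---|---|---|
| 0.50 / 0.50 | 1.00 | pass | pass |
| 0.50 / 0.25 | 0.50 | pass | fail |
| 0.50 / 0.39 | 0.78 | pass | fail |
| 0.50 / 0.61 | 1.22 | pass | fail |
| 0.507 / 0.507 | 1.00 | fail | pass |
| 0.493 / 0.493 | 1.00 | fail | pass |

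The rules disagree in both directions, so neither can stand in for the other.

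**2. How often exact equality could hold.** The product is 100 mg/mL (Protocol 6.1.1.1), so 0.5 g/kg is 5 mL/kg. The prescription is written in mL (Protocol 6.1.2.3) and vials hold 10 g or 20 g (Protocol 6.1.1.2). The documents give neither a rounding practice nor a weight precision, so both are assumptions here. If the volume is rounded to the nearest r mL, equality is exact only when 5 × weight is a multiple of r.

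For weights recorded to 0.1 kg:

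- r = 1 mL: weight a multiple of 0.2 kg, about 1 in 2 courses (50%);
- r = 5 mL (0.5 g): a multiple of 1 kg, about 1 in 10 (10%);
- r = 10 mL (1 g): a multiple of 2 kg, about 1 in 20 (5%);
- r = 50 mL (5 g): a multiple of 10 kg, about 1 in 100 (1%);
- r = 100 mL (a 10 g vial): a multiple of 20 kg, about 1 in 200 (0.5%).

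For weights recorded in whole kg, 5 × weight is always a multiple of 5 mL, so rounding to 1 or 5 mL gives 100%. The range is therefore about 0.5% to 100% of courses.

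The comparison precision matters as much. A simulation with assumed weights N(75, 14) kg, truncated to 45–120 kg and recorded to 0.1 kg, compared doses at two decimals. It gave about 99.8% of courses passing with 5 mL rounding, 75% with 10 mL and 8% with 100 mL. In all these scenarios every rounded dose stayed within 20% of 0.5 g/kg.

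**The all-courses rule.** With 16 courses and independent passes at probability q, patient compliance is q^16: 0.99^16 = 0.85, 0.95^16 = 0.44, 0.90^16 = 0.19, 0.80^16 = 0.03. Independence is doubtful because a patient's weight recurs. In the 10 mL, two-decimal scenario, 0.75^16 is about 1%. The simulated figure is about 75% if weight never changes and about 10–12% if it varies within patient with an SD of 0.5 to 2 kg. Sixteen is also a maximum, given relapse withdrawals and early termination.

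**The case against.** A reader might infer four stronger things, and the documents support none of them.

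*That the SAP ignores the administered dose, so under-dosing cannot be seen.* SAP 4.7.1 summarises cumulative dose, dose per course and dose per infusion from the administered volume and promises listings at patient, course and infusion level; SAP 5.6.2 defines the actual administered dose. The information is reported. What is missing is the compliance criterion.

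*That the compliance rate will be near zero.* That happens only under some combinations of weight precision, rounding and comparison precision. Others give 100%.

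*That testing the prescribed dose contradicts the protocol.* Protocol 12.8.2 has a prescribed-dose criterion too, worded as permitted ranges, though no numeric range around 0.5 g/kg is given. The conflict lies in the dropped ratio; the bare equality needs reconciling with that wording.

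*That the primary result is affected.* The responder definition does not use the compliance rule; it has its own 5% dose-change condition (SAP 2.5.1 and 4.6.1).

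Two further objections have force. The SAP's meaning of Prescribed is blurred: it refers to what is reported at each course and infusion, and SAP 4.7.1 applies both terms to a single volume. If Prescribed in fact meant the dose given, the half-dose example would fail the SAP criterion. Also, SAP 4.5 lists non-compliant courses and flags the failed criterion, so rounding failures would be visible. Neither restores the 20% comparison or declares its removal.

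**Conclusion.** The point holds as an undeclared departure from the protocol's compliance definition, combined with an equality check whose result depends on a rounding rule that is not stated. That the two rules disagree in both directions rests on reading Prescribed as the ordered dose, which the separate eCRF items imply. The pass rate under equality cannot be determined from the documents; the 0.5% to 100% span rests on assumed weight precision and rounding.

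The consequence is confined to the descriptive compliance table and listing on the Total Treated Set. It would reach the Per Protocol Set only if the protocol deviation specifications, which SAP 3.5.2 refers to but which are not in the documents, use this rule. It should be corrected, because a reduced-dose study needs a compliance figure that means what the protocol says it means.

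**What to change.** Three changes to the SAP:

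1. In SAP 4.5, add a per-course criterion that the administered/prescribed ratio lies between 0.80 and 1.20, taken from the two doses recorded separately in the eCRF, and make clear that Prescribed means the ordered dose. Otherwise, declare and justify the removal of this criterion in SAP 4.10.
2. Reconcile the equality check with the permitted-ranges wording of Protocol 12.8.2 by stating the precision at which the prescribed dose is compared with 0.5 g/kg.
3. Report the number of compliant courses per patient beside the all-courses flag, so that one failed course can be told from many.

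The cost is SAP wording and a small programming change before database lock. No new data are needed.

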### **5.4. Discontinuation Criteria / Stopping Rule(s)**

All patients are free to withdraw from participation in this study at any time, for any reason, and without prejudice. The Investigator must withdraw from the study any patient who requests to stop participating in the study. Patients who withdraw their consent will be asked to undergo the study assessments scheduled at the EOS visit. They will be advised that participation to the EOS visit is voluntary but is their best interest.

The Investigator must discontinue study drug administration to a patient and perform an EOS visit at the request of the Sponsor or if the patient:

- Experiences an AE - including a clinically significant laboratory abnormality -that justifies study drug premature discontinuation.
- Undergoes protocol deviation that could endanger the patient safety.
- Becomes pregnant.
- Relapses.

Relapsing patients will undergo the study assessments scheduled at the EOS visit within 7 days and prior to the administration of any other CIDP treatment. The patient will be then withdrawn from the study and treated at the discretion of his/her physician.

If a patient is prematurely discontinued, the date, reason of discontinuation and any change in CIDP treatment will be documented.

If a patient is withdrawn because of an AE, he/she will be followed up until complete resolution or stabilisation of the AE.

Patients lost to follow-up will be considered as discontinued from the study. A patient will be considered as lost to follow-up only after having exhausted all means of contact. Investigators must make every effort to contact the patient and/or his/her family or relatives to obtain the maximum of the per protocol requested information. All contact attempts should be documented in the patient's medical records

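### SAP 4.5 omits two of the protocol's four compliance criteria, so a patient whose last due course was missed is reported as fully compliant

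*SAP*

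**What the plan says.** Protocol 12.8.2 names four criteria to be described: prescribed dose within the allowed range; "Course frequency included in the ranges allowed by the protocol"; "Courses administered at each visit"; and "Ratio administered dose / prescribed dose within 20" percent. The last is also how protocol section 6.1.3.4 defines compliance with treatment.

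SAP 4.5 lists five course-level criteria: prescribed dose equal to 0.5 g/kg; "Time since previous course = 3 weeks" ± 7 days; "Courses administered within 1 to 2 days"; and two checks on the initial flow rate of a course. The patient-level rule is "Total patient compliance: A patient is compliant if all courses of the patient are compliant". The SAP defines a term for planned dose and frequency, but no criterion uses it. The prescribed dose and frequency are what "refers to the treatment dose and frequency reported at each IMP course and infusion".

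SAP 4.10, which records changes to the planned analysis, does not mention compliance.

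Protocol 5.4 makes relapse a reason to stop: "The Investigator must discontinue study drug administration to a patient and perform an EOS visit at the request of the Sponsor or if the patient" meets one of the listed conditions, relapse among them. Protocol 8.2.2 to 8.2.4 place the INCAT assessment before the course at each visit.

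**The concern.** Every SAP 4.5 criterion is a property of a course that took place, and nothing compares courses given with courses due. The only sign of a missed course is the interval check, which looks back from the next course. If no next course follows, the long gap is never measured. Because INCAT is scored before the infusion and relapse stops study drug, a patient who misses a course and is found in relapse at the next visit falls into this gap. So does a patient who misses V16 and then attends V17.

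The same table cannot show a course that was only partly given, because only the prescribed dose is checked.

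The trial asks whether the reduced maintenance regimen sustains response, and SAP 4.10 reports that it was terminated early because of relapses at that dose. Readers will look to the compliance table to see whether the patients who relapsed had received the regimen. A relapse after a missed course cannot be attributed cleanly to the dose, and this is where the table can be wrong.

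**Working it through.** **Inputs.** 16 courses every 3 weeks ± 7 days (protocol 3.1.4); EOS visit at week 48 (protocol 3.1.5); allowed interval 21 ± 7 days, that is 14 to 28 days (SAP 4.5); 15 to 30 patients expected (protocol 12.3).

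**The plan's own figures.** (16 − 1) × 3 = 45 weeks of treatment and 16 × 3 = 48 weeks to EOS. Both match the protocol. Course k is therefore due on day 21 × (k − 1).

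**The two lists side by side.**

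| Protocol 12.8.2 | SAP 4.5 |
|---|---|
| Prescribed dose in range | Prescribed dose = 0.5 g/kg |
| Course frequency in range | Time since previous course 14 to 28 days |
| Course given at each visit | No counterpart |
| Administered/prescribed within 20% | No counterpart |
| Not listed | Course length; two flow-rate checks |

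**Case A: course k missed, treatment resumes (k = 2 to 15).** The next interval is nominally 42 days, above 28, so 14 of 14 cases are flagged. If the courses on either side each move by whole days from −7 to +7, the gap runs from 42 − 14 = 28 to 42 + 14 = 56 days. Only 1 of 15 × 15 = 225 combinations gives exactly 28 days and passes.

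**Case B: course k missed, no further course (k = 2 to 16).** No later interval exists. If the courses given meet the other criteria, 15 of 15 cases are fully compliant under SAP 4.5. Under the protocol's attendance criterion, 0 of 15 are.

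**Example.** V1 to V5 are given (days 0 to 84), V6 (day 105) is missed, and relapse is found before infusion at V7 (day 126). The 126 − 84 = 42-day gap is never tested. SAP 4.5 shows 5/5 = 100%; courses given over courses due is 5/6 = 83%. V7 is not counted as due, because relapse was established before that infusion. For a missed V16 followed by V17, the SAP shows 15/15 against 15/16 = 94%.

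**Partly given course.** Assume a two-day course prescribed at 0.5 g/kg, split equally, with the second day not given. Administered/prescribed is 0.25/0.5 = 50%, outside the protocol's 20% limit. The SAP dose criterion still passes, because the prescribed dose is 0.5 g/kg.

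**Size.** One misclassified patient moves the patient-level compliance percentage by 1/30 = 3.3 to 1/15 = 6.7 points.

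**The case against.** The strongest reply is that the information is not lost. SAP 4.7.1 uses the EOS date to close the last interval in average course frequency, so that average equals (EOS − first course)/number of courses and includes a terminal gap. Total courses and exposure duration are reported alongside it and listed by patient. SAP 3.5.2 covers deviations regarding study drug and visit windows, SAP 4.2 tabulates them as minor or major, and major deviations remove a patient from the PPS, on which the primary analysis is repeated. This stands as far as it goes. But the average dilutes the gap: 126/5 = 25.2 days in the example, and 336/15 = 22.4 days for a missed V16. Both lie inside 14 to 28 days, and no threshold is applied to the average. The deviation specifications are a separate document, so a missed-course rule there can be neither assumed nor ruled out. Neither output corrects a compliance table that shows 100%.

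Second, the 1-to-2-day check is itself a protocol requirement (3.1.4), and the SAP nowhere says that it stands in for attendance. That is right: the omission is established by comparing the lists, while a deliberate substitution is not. That a course not given has no row is likewise inferred from the patient rule; the SAP does not say how such a course is recorded.

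Third, protocol 12.2 sends changes from the protocol to the study report, so silence in SAP 4.10 is not in itself a breach. This also stands, but SAP 4.10 does list other changes, and a reader would expect this one there.

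A reader might infer that missed courses in general go undetected. Case A shows that they do not when treatment resumes.

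**Conclusion.** The point holds for a missed course that is followed by no further course, and for the omitted administered/prescribed ratio. In the first case the rule as written returns full compliance for a patient who missed a due course, in all 15 positions where this can happen. The effect is 3.3 to 6.7 points of the patient-level compliance percentage per affected patient, given 15 to 30 patients and courses that otherwise met the criteria. The number of affected patients is unknown and may be zero.

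A reader might go further and infer that the relapse fraction or the responder rate is distorted. The documents do not support that: SAP 4.5 feeds neither the responder definition, nor the Kaplan-Meier analysis, nor the PPS, and a relapse remains a relapse whatever the compliance row shows. It would also be wrong to measure a missed course against the 5% dose-change rule in SAP 4.6.1, which concerns the g/kg dose as a change in CIDP treatment, or against the 33.6-day half-life in protocol 1.3.2, which comes from immunodeficiency patients and is not linked to relapse. Nor do the documents show that any relapse in this trial followed a missed course.

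This is a defect in a descriptive table of a study without hypothesis tests. It should be fixed because that table bears on how the relapses are read, and the repair is small.

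**What to change.** In SAP 4.5:

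- Restore the attendance criterion: derive course given Yes/No for every visit due up to the relapse or discontinuation decision, and count a due visit without a course as non-compliant. Do not count a course withheld because relapse was already established.
- Report courses given / courses due per patient.
- Restore the administered/prescribed ratio within 20%.
- For patients who relapse, list the days from the last infusion to the assessment at which relapse was first found, and flag intervals above the SAP's own 28 days. Do not use a later EOS visit as the end date. Protocol 3.1.6 allows 7 days for those assessments, so a patient with no missed course could show 28 + 7 = 35 days.

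Declare any remaining departure from protocol 12.8.2 in SAP 4.10.

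The cost is SAP wording and a few derived rows. Protocol section 6.1.3.3 already has the prescribed dose, the administered dose, and the date and time of administration recorded in the eCRF. The compliance figure may become slightly less favourable.

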#### **6.1.3. 2. Method of administration**

Before administration to a patient, the Investigator will check that the label corresponds to his/her prescription for the patient (study number, patient number, study drug dose).

Study drug will be administered with an infusion pump.

The infusion flow rate must be compliant with the Investigator's Brochure of I10E.

For the first day of any study drug course, the initial flow rate will not exceed 0.5 mL/kg/h during the first 30 minutes. If well tolerated, the rate of administration may be increased up to 1 mL/kg/h during 30 minutes, then, at the Investigator's discretion, gradually increased up to 2, 4 and 6 mL/kg/h as a maximum flow rate. In patients older than 65 years, the maximum infusion flow rate should be 2 mL/kg/h.

On the subsequent days of any study drug course, the flow rate is at the Investigator's discretion (up to 6 mL/kg/h except for patients older than 65 years for whom the maximum infusion flow rate should be 2 mL/kg/h).

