#### **6.1.3. 3. Traceability, Accountability and Documentation**

Each study drug course should be documented in the patient's medical file, including doses, time and flow rate changes.

The prescribed dose, the date and time of administration and the exact dose administered will be recorded in the eCRF.

The Sponsor will provide specific forms for IMP accountability, which will be kept up-to-date by the Hospital Pharmacist throughout the study. At the end of the study, it must be possible to reconcile the number of study drugs sent by the drug distributor with the number of study drugs delivered to patients and the number of unused study drugs.

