### **9.3. Risk Minimisation Actions Throughout the Protocol**

Some adverse drug reactions may be related to the infusion flow rate. Patients will be closely monitored and carefully observed for any symptoms throughout the infusion periods. In the case of AE, the infusion rate may be reduced or even stopped. Standard medical care should be implemented as necessary.

Potential complications will be avoided by ensuring that patients:

- have an adequate hydration status prior to infusions of the study drug;
- are not sensitive to human normal Ig by initially infusing the product slowly, starting at 0.5 mL/kg/h during the first 30 minutes;
- are carefully monitored for any symptoms throughout the infusion period and 30-45 minutes after the end of each infusion. An additional phone call at 4 days (+/- 1 day) from the Investigator or the Study Nurse to the patient is planned to ask if AEs or TAAEs are reported within 72 hours after the end of each course;
- Close Monitoring (vital signs, biological tests, haematological tests, physical examinations planned for each course to minimise these risks);
- D-Dimers, in case of suspected thrombus;
- Reticulocytes and Direct Coombs test, in case of haemolysis based on biological tests [Hb, haptoglobin, LDH, total and free bilirubin levels (total bilirubin in all patients; if total bilirubin > ULN, free bilirubin will be assessed from the same blood sample, as total bilirubin)].

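### SAP 4.5's two flow-rate criteria approximate only the first 30-minute ceiling: permitted early slowing scores as non-compliant, while a breach of the maximum rate scores as compliant

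*SAP*

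**What the plan says.** Protocol 6.1.3.2 states the rates as upper limits. On the first day of any course "the initial flow rate will not exceed 0.5 mL/kg/h during the first 30 minutes". If tolerated, the rate may then rise to 1 mL/kg/h for 30 minutes, and after that gradually through 2 and 4 to a maximum of 6 mL/kg/h. The maximum is 2 mL/kg/h in patients older than 65. On later days of a course the rate is left to the investigator, within the same two maxima. Protocol 9.3 allows slowing: "In the case of AE, the infusion rate may be reduced or even stopped".

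SAP 4.5 lists five course-level compliance criteria, two of them about rate:

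- One on how long the early rate is held: "Duration of the flow rate of the first course infusion remains unchanged for at least 25 minutes".
- One on the level of that rate: "Flow rate of the first infusion of a course" at most 0.5 mL/kg/h.

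The patient-level rule is "Total patient compliance: A patient is compliant if all courses of the patient are compliant". Non-compliant courses and infusions are listed with the failing criterion flagged.

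SAP 4.7.1 summarises the following as exposure: the initial rate of a course's first infusion and how long it lasted, the maximum rate at patient, course and infusion level, and the number of rate changes per infusion. It compares none of these with a limit.

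**The concern.** The protocol limits how fast the drug may run. SAP 4.5 tests whether the early rate stayed constant and whether it was low. These differ in two ways that matter for the compliance output.

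- **False non-compliance.** A change before 25 minutes fails even if the rate never exceeds 0.5 mL/kg/h. Slowing for an adverse event is such a change.
- **False compliance.** Nothing in SAP 4.5 looks at the maximum rate, at age, or at any infusion after the first of a course.

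The all-courses rule amplifies the first error: one slowed course out of up to 16 makes the patient non-compliant. Rate is a safety matter in this protocol. Section 9.3 links some adverse reactions to flow rate, and section 9.2.1 names age over 65 among the risk factors for acute renal failure. A table that appears to cover infusion rate but omits the age-specific cap could mislead a reader of the safety results.

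The second criterion also lacks the word 'initial' and any time window, so as worded it would fail a course that follows the protocol's own step-up.

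**Working it through.** The plan gives no figure to reproduce, so the check runs rate profiles against both sets of rules.

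**Inputs.** Course dose 0.5 g/kg (SAP 4.5; Protocol 6.1.3.1). Concentration 100 mg/mL = 0.1 g/mL (Protocol 6.1.1.1). Rate ceilings from Protocol 6.1.3.2. One-day course unless stated.

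**Volume.** 0.5 / 0.1 = 5 mL/kg.

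**First hour at the protocol ceilings.** 0.5 × 0.5 h + 1 × 0.5 h = 0.75 mL/kg, leaving 4.25 mL/kg.

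**Shortest permitted one-day course, older than 65.** 60 + (4.25 / 2) × 60 = 187.5 min.

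**Step-up to 6 mL/kg/h, assuming 30 minutes each at 2 and 4.** Volume at 120 min = 0.75 + 1 + 2 = 3.75 mL/kg. The remaining 1.25 mL/kg takes (1.25 / 6) × 60 = 12.5 min, for a total of 132.5 min. The protocol gives no durations for the 2 and 4 steps. Going straight from 1 to 6 mL/kg/h at 60 min gives 60 + (4.25 / 6) × 60 = 102.5 min, a lower bound that a gradual increase cannot reach.

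**Profiles, with the second criterion read as the initial rate.**

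| Rate profile (mL/kg/h) | Total min | Protocol | SAP rate pair |
|---|---|---|---|
| 0.5/1/2/4/6 in 30-min steps, age 65 or less | 132.5 | met | pass |
| 0.5/1/2, older than 65 | 187.5 | met | pass |
| 0.5, cut to 0.25 at 10 min, 0.5 at 30, 1 at 60 | 335 | met | **fail** |
| 0.3, 0.5 at 15 min, 1 at 30, 2 at 60 | 189 | met | **fail** |
| 0.5/1/2/4/6 in 30-min steps, older than 65 | 132.5 | breached | **pass** |
| 0.5/1/2, then 8 at 90 min, age 65 or less | 114.4 | breached | **pass** |
| Start at 1 | 180 | breached | fail |
| 0.5, then 1 at 10 min | 182.5 | breached | fail |

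The last two rows show what the pair does well: it catches breaches of the first ceiling. The four rows in bold are misclassified.

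**Second infusion day** (assumed even split, 2.5 mL/kg), older than 65. At the cap: 2.5 / 2 × 60 = 75 min. At 6 mL/kg/h: 2.5 / 6 × 60 = 25 min. Neither rate criterion applies to this infusion.

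**Second criterion exactly as worded.** Only an infusion held at or below 0.5 mL/kg/h throughout passes: 5 / 0.5 = 10 h = 600 min for a one-day course.

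**Age.** SAP 5.6.3 derives age at screening, and SAP 4.3 takes age from I10E-1302. The gap to the week-45 dose is at least 21 + 45 = 66 weeks, or 462 / 365.25 = 1.26 years, so a patient can pass 65 in between.

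**The case against.** The strongest defence is that SAP 4.7.1 already pairs the initial rate of the first infusion with its duration, and the two SAP 4.5 bullets follow that pair. On that reading they test the first 30-minute ceiling with a 5-minute recording tolerance. This stands. A reader might infer that the criteria measure none of the protocol's ceilings, or that every stepped-up course would be failed. The documents do not support either: a check that the early rate is unchanged for 25 minutes presupposes a later change, so the missing 'initial' is probably a wording lapse.

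It is also fair that rate is not a compliance criterion in Protocol 6.1.3.4 or 12.8.2, and that Protocol 12.8.1 places initial and maximum rate under exposure. SAP 4.7.1 follows it, and its infusion-level listing includes second days. SAP 3.5.2 has a deviation category for the study drug, whose specifications are not among the documents. So it would be wrong to infer that cap breaches go unreported in the trial. But the exposure output applies no threshold or age split, and a deviation review does not correct the SAP 4.5 table. Having added rate checks, the SAP should align them with the protocol's limits.

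Finally, early slowing may be uncommon in patients who tolerated higher doses in I10E-1302, and slowed courses would be visible in the listing. That limits the size of the first error but leaves the classification wrong.

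**Conclusion.** The concern holds in a limited form, at minor severity. Read charitably, SAP 4.5 approximates one of the protocol's rate ceilings. It misclassifies permitted early changes as non-compliant. It also scores maximum-rate breaches as compliant if the other criteria are met, including the over-65 cap and any second-day infusion.

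The size is illustrated by a one-day course in a patient older than 65: about 132.5 minutes (30-minute steps assumed) passes both rate criteria where the cap requires at least 187.5. The documents do not allow the number of affected courses to be estimated.

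A reader might infer an effect on efficacy or on the analysis sets. The documents do not support that. The response definition in SAP 4.6.1 does not use infusion rate, and the SAP 3.5.1 populations do not refer to SAP 4.5 compliance. Only the descriptive compliance table and the non-compliance listing change.

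**What to change.** 1. **First-infusion criterion.** Reword it as the initial flow rate of the first infusion of a course, at most 0.5 mL/kg/h. Label 25 minutes as a recording tolerance on the 30-minute step. Do not count reductions or stops as failing the rate criterion where the eCRF records the new rate. Where it does not, list the early change as 'direction not recorded' rather than non-compliant.
2. **Maximum-rate criterion.** For every infusion, require the maximum flow rate to be at most 6 mL/kg/h, or 2 mL/kg/h if the patient is older than 65 on the infusion date.
3. **Second step.** State that the 1 mL/kg/h step is not tested unless timed rate changes are in the database. Protocol 6.1.3.3 says "Each study drug course should be documented in the patient's medical file, including doses, time and flow rate changes", and does not name rate changes among the items recorded in the eCRF.

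**Cost.** Item 2 uses a maximum rate already derived at infusion level in SAP 4.7.1, plus age on the infusion date. Item 1 needs the value or direction of the first rate change, which SAP 4.7.1 does not list; hence the fallback. The downside is slight extra programming and a possibly less favourable compliance rate.
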